4 LIST OF ABBREVIATIONS

ADR	Adverse Drug Reaction
AE	Adverse Event
ALT	alanine aminotransferase/serum glutamic pyruvic transaminase (SGPT)
ANOVA	Analysis of variance
AST/SGOT	Aspartate aminotransferase
ATD	Anticipated Therapeutic Dose Range
AUC	Area Under the Curve
BASO	Basophil
B-OT	Benfo-oxythiamine
BMI	Body Mass Index
BP	Blood Pressure
Bpm	beats per minute
BUN	Blood Urea Nitrogen
CA	Competent authority
Cl/F	Clearance
C _{max}	Maximum concentration
EC	Ethics Committee
eCRF	electronic Case Report Form
EOS	Eosinophil
CSP	Clinical Study Protocol
CSR	Clinical Study Report
CV	Coefficient of Variation
DBP	Diastolic Blood Pressure
DCC	Diagnostics and Consultation Centre
DMP	Data Management Plan
EC	Ethics Committee
ECG	Electrocardiogram
EDTA	Ethylene Diamine Tetra-acetic Acid
EOS	End of study
EU	European Union
FIH	First in human
GCP	Good Clinical Practice
GLP	Good Laboratory Practices
Gamma-GT	Gamma-glutamyltransferase
HCT	Hematocrit
HGB	Hemoglobin
Hem	Hematology
Hep B	Hepatitis B
Hep C	Hepatitis C
HIV	Human Immunodeficiency Virus

HR	Heart Rate
hr.	Hour
IB	Investigator's Brochure
ICF	Informed Consent Form
ICH	International Conference on Harmonization
IMP	Investigational Medicinal Product
kg	Kilogram
LLOQ	Lower Limit of Quantification
LYMP	Lymphocyte
MAD	Multiple Ascending Dose
MedDRA	Medical Dictionary for Regulatory Activities
MCV	Mean Corpuscular volume
MCH	Mean Corpuscular Haemoglobin
MCHC	Mean corpuscular haemoglobin concentration
MONO	Monocyte
NEUT	Neutrophil
NOAEL	No Observed Adverse Effect Level
OTC	Over-the-counter
OT	Oxythiamine
PAD	Pharmacologically Active Dose
PD	Pharmacodynamic
PE	Physical examination
PI	Principal Investigator
PK	Pharmacokinetic
PLT	Platelet
PPP	Pentose phosphate pathway
PR	Pulse Rate
PT	Preferred Term
RBC	Red Cell Count
R5P	Ribose-5-Phosphate
SAD	Single Ascending Dose
SAE	Serious Adverse Event
SAP	Statistical Analysis Plan
SAR	Serious Adverse Reaction
SAS	Statistical Analysis Software
SOC	System Organ Class
SOP	Standard Operating Procedure
SRC	Safety Review Committee
SUSAR	Suspected Unexpected Serious Adverse Reaction
TEAE	Treatment Emergent Adverse Event
TK	Toxicokinetic

TKT	Transketolase
TKTL1	Transketolase-like 1
$t_{1/2}$	Terminal half life
t_{\max}	Time of the maximum concentration
UADR	Unexpected Adverse Drug Reaction
UAE	Unexpected Adverse Event
ULOQ	Upper limit of quantification
WBC	White Cell Count
WHO	World Health Organization

[figure not shown]
5 PROTOCOL SYNOPSIS

Study Title	Assessing the safety, tolerability and pharmacokinetics of B enfo- O xythiamine (B-OT) in healthy volunteers – An O pen label, phase I S tudy
Study Type	Monocentric, open label, first-in-man phase I study
Protocol No. / Short Title	BV-01-101 / BOOST
EUDRA-CT No	2021-005616-60
Targeted Indication	SARS-CoV-2 infection / Covid-19
Investigational Drug	Benfo-oxythiamine (B-OT) B-OT is a novel thiamine analogue, which functions as a prodrug and releases oxythiamine in the human body. The introduction of a benfo group into a molecule improves its cell permeability and may ensure better bioavailability. The thiamine antagonist oxythiamine is an irreversible inhibitor of thiamine-dependent enzymes, such as transketolases, and efficiently inhibits the sugar metabolism and the accumulation of Ribose-5-Phosphate (R5P) building blocks.
Sponsor	benfovir AG [name]

Objectives and end point	
Primary Objectives:
 
To assess the safety and tolerability of single and multiple ascending doses of B-OT
 
 • Endpoints: 
 ○ safety evaluations including safety laboratory assessments, physical examination (PE), electrocardiograms (ECGs), vital signs, adverse events (AEs) and serious adverse events (SAEs). 
Secondary Objectives
 
 • To evaluate the pharmacokinetics (PK) of benfo-oxythiamine (B-OT) and its active metabolite oxythiamine (OT) in plasma following single doses administered to healthy volunteers • To evaluate the pharmacokinetics (PK) of benfo-oxythiamine (B-OT) active metabolite oxythiamine (OT) in plasma following multiple doses administered to healthy volunteers. • Endpoints: 
 ○ SAD: Plasma PK parameters, including C_{max}, t_{max}, t_{1/2}, CL/F, λ_z, V_z/F, AUC_{0-inf} and AUC last as appropriate ○ MAD: The following PK endpoints will be derived from plasma oxythiamine (OT) concentration versus time data following administration according to the dosing schedule on Day 1: AUC_τ, C_{max}, t_{max}, on Day 7: AUC_τ, C_{max,ss}, t_{max,ss}, Swing, PTF%, CL_{ss}/F, V_z/F, C_{trough}, C_{av}, C_{min}, t_{1/2}, AUC_{inf} and AUC_{last} as appropriate and Day7/Day1: Ra(AUC_τ), Ra(C_{max}). 
Exploratory Objectives
 
 • To evaluate the pharmacodynamics (PD) by measuring the transketolase activity in • To analyse PK parameters of other B-OT derivative metabolite(s), if any.
---------------------------------	---


Study Design,
 
Mode of administration,
 
starting dose and dose level,
 
Stopping rule
	
This is a monocentric, open-label, non-randomized, uncontrolled, first-in-human study to assess the safety, tolerability, and pharmacokinetics /pharmacodynamics of B-OT in healthy subjects.
 
This study has two parts: a single ascending dose (SAD) part and a multiple ascending dose (MAD) part.
 
Administration and dose levels:
 
First Part of the study: SAD
 
In the SAD part, a single dose of B-OT will be administered per oral (p.o.) once daily on day 1 followed by 7 days without dosing.
 
Up to 5 cohorts will be enrolled and dosed. Dosing is based on NOAEL x HED x 1/10 (No Observed Adverse Effect Level x Human Equivalent Dose [dog/human] x Safety Factor). As NOAEL was established in dog after a 7-day treatment and B-OT has already been used in compassionate use at a minimum daily dose of 3 mg for 7 days in 5 Covid-19 patients and 5 late-stage prostate cancer patients without any safety issue, only 3 subjects will receive the two first lowest doses.
 
The first dose of B-OT will be 0.5 mg (0.0083 mg/kg body weight, average 60 kg adult). After the first cohort, enrolment will be halted. If no safety issue is observed, the second dose level will be 1 mg (0.016 mg/kg body weight). The first and second dose level cohort will have 3 subjects. The human PK/PD model will be refined before enrolling to the next dose level. As this is the first study testing B-OT in humans, study design adjustments may be made based on emerging data from each dose cohort based on review of preliminary safety, tolerability, and PK/PD results. If these data allow for, the dose escalation scheme of 2 mg, 3 mg and 5 mg will follow in 3 additional cohorts of 6 subjects.
 
Each cohort will start with a sentinel subject (subject #1).
 
Subject #2 - #3 or #2 - #6 of the same cohort will start treatment after a minimum of 48 hours if safety data indicate that dosing of subsequent subjects of this cohort is justified.

---	---

The following figure represents the study design of the SAD part:

The filled box represents a dosing event, a white box a represents a dosing free day. Single dose treatment will be administered on Day 1.

Dose escalation to the next dose level will occur if three (first and second cohort) or six subjects (3 next cohorts) have completed the single dose treatment and if PK as well as safety data allow an escalation to the next dose level.

[figure not shown]
Second Part of the study: MAD

In the MAD part, a single dose of B-OT will be administered orally (*p.o.*) once daily for 7 days (D1-D7) followed by 7 days without dosing. The first dose will be 1 mg, as the PK and safety data in the SAD part of the study have shown an acceptable safety margin at this dose (see IB).

Each cohort will start with a sentinel subject (subject #1).

Subjects #2 - #6 of the same cohort will start treatment after a minimum of 72 hours if no adverse event is observed in the sentinel subject.

The following figure represents the study design of the MAD part:

	 
■ Dosing event □ Dosing free day
 
Definite Stopping rules
 
Dose escalation will not continue to the next dose level if (a) maximal OT plasma levels are achieved, i.e. further increase is not justified from a scientific point of view, or if (b) toxicities are observed that do not justify continuation from an ethical point of view.
 
The study will be halted if one or more subjects experience a serious adverse event (SAE) that is considered as related to B-OT or 2 or more subjects in the same group experience severe AEs that are considered to be related to B-OT.
 
Dose-escalation will stop if clinically relevant signs or symptoms of similar nature occur in 2 or more subjects in a group that, in the opinion of the PI, warrant stopping of dose-escalation.

Inclusion criteria	
Subjects will be enrolled if they meet all the following inclusion criteria:
 
 - Signed and dated informed consent form - Subjects capable to understand the purposes and risks of the study, and who are willing and able to participate in the study - Male volunteers who are willing to comply with contraception requirements - Aged 18-60 years, inclusive - Healthy participants, as determined by screening assessments and Principal Investigator's judgment - Healthy status is defined by the absence of evidence of any active or chronic disease following a detailed medical and surgical history, a complete physical examination including vital signs, 12-lead ECG, hematology, blood chemistry, serology, and urinalysis - Body Mass Index (BMI) of 18-30 kg/m² inclusive 
Contraception Requirements

	
 - Male participants with female partners of childbearing potential are eligible to participate if they agree to one of the following during the protocol defined time frame: - Be abstinent from penile-vaginal intercourse as their usual and preferred lifestyle (abstinent on a long term and persistent basis) and agree to remain abstinent - Use a male condom plus partner use of a contraceptive method with a failure rate of < 1% per year when having penile-vaginal intercourse with a woman of childbearing potential who is not currently pregnant. 
Note: Men with a pregnant or breastfeeding partner must agree to remain abstinent from penile-vaginal intercourse or use a male condom during each episode of penile penetration.

Exclusion criteria	
 - Subjects who meet any of the following exclusion criteria at Screening (unless otherwise stated) will not be eligible for participation: - Subjects who have a clinically relevant history as determined by the Investigator, or presence of respiratory, gastrointestinal, renal, hepatic, hematological, lymphatic, neurological, cardiovascular, psychiatric, musculoskeletal, genitourinary, immunological, dermatological, endocrine, connective tissue diseases, or disorders. - Fridericia's correction factor for QT (QTcF) > 450 ms or history of QT interval prolongation. - Have acute gastrointestinal symptoms (e.g., nausea, vomiting, diarrhea, heartburn) at the time of screening or admission. - Has any abnormal laboratory value of Grade 2 or higher, which is considered as clinically significant by the PI (or designee). - Has values of $\geq 10\%$ above the upper limit of normal for the following laboratory analytes: 
 - alanine aminotransferase (ALT/SGPT), alkaline phosphatase (serum), aspartate aminotransferase (AST/SGOT), at Screening and Day-1 - creatinine and urea concentration in blood at Screening and Day-1 - Have a clinically relevant surgical history, as determined by the Investigator. - Have a history of relevant drug hypersensitivity. - Have a history of alcoholism or drug abuse. - Have a significant infection or known inflammatory process at screening or admission.

	
 - Have used any prescription or non-prescription medicines within 2 weeks of admission, unless in the investigator's opinion it will not affect the determination of safety or other study assessments. - Have received any investigational drug within 30 days prior to screening. - Have used tobacco or nicotine products within 3 months of screening - Has a positive alcohol or drug screen at Screening or the Day1 visit - Have donated or received any blood or blood products within the 3 months prior to screening. - Cannot communicate reliably with the investigator. - Have been vaccinated with a Covid-19 vaccine within 2 weeks prior to screening and/or during participation in the clinical trial - Are unlikely to co-operate with the requirements of the study.
Statistical considerations and sample size	
The study is exploratory and is not powered to address any pre-defined hypotheses. The assessment of safety and tolerability will be performed on the safety analysis set, which includes all subjects who received at least one dose of B-OT. Complete description of all statistical analyses and methods will be presented in the Statistical Analysis Plan (SAP). The SAP will be reviewed and approved by the Sponsor and will be finalized prior to database lock. Plans for PK analyses will be included in the SAP.
 
Determination of Sample Size:
 
The sample sizes for the SAD and MAD cohorts are typical for a Phase 1 first in human (FIH) study.
 
The total number of subjects accrued in the study will depend on the number of dose levels, but is currently set to a maximum of 48 subjects (in the SAD: 2 cohorts with 3 subjects and 3 cohorts with 6 subjects each and in the MAD: 4 cohorts of 6 subjects each). The safety and tolerability of B-OT will be analyzed by appropriate descriptive statistics. All other secondary endpoints will be summarized descriptively.
 
Study Populations:
 
Safety Population: All subjects who receive at least one dose of study drug.
 
Pharmacokinetic Population: All subjects receiving study drug who comply sufficiently with protocol requirements (i.e., no major protocol deviations) and for whom enough analyzable PK samples have been obtained to allow the determination of the PK profile for B-OT/OT and the statistical analysis of the results.

	
Safety Analyses: Statistical methods for the safety analyses will be descriptive in nature. Safety data, including AEs, clinical laboratory data, vital signs, ECG parameters, and PEs. All appropriate AEs will be graded using the DMID toxicity scale (March 2014). Change from baseline will be included in summary tables for laboratory parameters. All laboratory data will be included in the data listings and all test values outside the normal range will be flagged.
 
Pharmacokinetic Analyses: Plasma PK parameters for each dose level in the SAD part of the study will be calculated from the concentrations of B-OT and OT measured in pre-dose and post-dose plasma samples. For each dose level, descriptive statistics will be presented. Figures will be created to display mean and individual subject B-OT and OT concentration versus time. Plasma PK parameters for each dose level in the MAD part of the study will be calculated from the concentrations of OT and possible derivate metabolites. Figures will be created to display mean and individual subject OT concentration versus time.
 
Interim Analyses: No formal interim analyses are planned for this study. Data from SAD cohorts were frozen and analyzed prior to conducting the second MAD part of the study.

--	--

TABLE 1: VISIT AND ASSESSMENT SCHEDULE OF THE SINGLE ASCENDING DOSE PART

Visit	Screening (Days -28 to -2)	Day -1	Day 1 (T=0)	Day 2 (24 hr) +/- 30min	Day 3 (48 hr) +/-1hr	Day 4 (72 hr) +/-1hr	Day 8 (EOS) (168 hr) +/-2hr	
Informed consent	x							
Demography	x							
I/E; Medical history	x	x						
Physical examination-PE ¹	x	x	x ²	x		x	x	¹ : a complete PE will be performed at Screening and/or Check-in and EOS; on all other days, a limited PE will target any change from the previous status, or any body system deemed pertinent to that subject by the PI (or designee) ² : at 4 hr post-dose
Vital signs ³	x	x	x	x	x	x	x	³ : vital signs include pulse rate, respiratory rate, blood pressure and body temperature; on Day1, VS should be taken pre-dose and at 2,4, 8 and 12 hr post-dose
Laboratory assessment (hematology, biochemistry)	x	x ⁴		x		x	x	⁴ : Results for safety blood samples must be available and reviewed before drug is administered
Urine analysis	x	x		x	x	x	x	
ECG	x		x ⁵	x			x	⁵ : the baseline ECG should be conducted prior to dosing on day 1
SARS CoV antigen	x						x	
SARS CoV PCR		x				x		

Study Protocol

Study number: BV-01-101

Version No. : 3.0

Date: 13 Jul 2022

Visit	Screening (Days -28 to -2)	Day -1	Day 1 (T=0)	Day 2 (24 hr) +/- 30min	Day 3 (48 hr) +/-1hr	Day 4 (72 hr) +/-1hr	Day 8 (EOS) (168 hr) +/-2hr	
Viral screening (HIV, Hepatitis)	x							
Drug screening	x	x					x	
Breath alcohol test	x	x					x	
Weight/height (BMI)	x	x ⁶					x ⁶	⁶ : only weight on Day -1 and 8
Confinement		x	x	x	x	x		
Ambulatory visit	x						x	
Administer study drug			x ⁷					⁷ : T=0 is time of drug administration
Plasma PK sample collection			x ⁸	x ⁹	x ⁹	x ⁹	x ⁹	⁸ : PK samples should be collected pre-dose and at 0.25, 0.5, 0.75, 1, 1.5, 2, 4, 8, 12 hr. depending on ongoing PK data review, timepoints may be modified or removed. ⁹ : PK samples should be collected at 24, 36, 48, 72 and 168 hr post-dose on Day 2, 3, 4 and 8
PD (TKT activity)			x ¹⁰	x	x	x	x	¹⁰ : on Day 1, TKT blood sample should be taken pre-dose and at 1, 2, 4, 8, and 12 hr and then at 24, 48, 72 and 168 hr post-dose.
Adverse Events	x ¹¹	x ¹¹	x ¹¹	x	x	x	x	¹¹ : Adverse events occurring prior to study drug administration should be recorded as medical history unless the event is directly related to study specific procedure
Prior and/or Concomitant medications	x	x	x	x	x	x	x	

CONFIDENTIAL

Study Protocol

Study number: BV-01-101

Version No. : 3.0

Date: 13 Jul 2022

TABLE 2: VISIT AND ASSESSMENT SCHEDULE OF THE MULTIPLE ASCENDING DOSE PART

Visit	Screening (Days -28 to -2)	Day -1	Day 1	Day 2	Day 3	Day 4	Day 5	Day 6	Day 7	Day 8	Day 11	Day 14 (EOS)	
Informed consent	x												
Demography	x												
I/E; Medical history	x	x											
Ambulatory visit	x										x	x	
Confinement		x	x	x	x	x	x	x	x	x			
Administer study drug			x	x	x	x	x	x	x				
Physical examination-PE ¹	x	x	x	x	x	x	x	x	x	x	x	x	¹ : a complete PE will be performed at Screening and/or Check-in and EOS; on all other days, a limited PE will target any change from the previous status, or any body system deemed pertinent to that subject by the PI (or designee)
Vital signs ²	x	x	x	x ³	x	x	x ³	x	x ³	x	x	x	² : vital signs include pulse rate, respiratory rate, blood pressure and body temperature; if not otherwise indicated, VS should be taken either at pre-dose on dosing days or at time of visit on ambulatory visit days ³ : on Day 2, 5 and 7, VS should be taken pre-dose and at 4 hr post-dose
Laboratory assessment (hematology, biochemistry, coagulation)	x	x ⁴		x ⁴			x ⁴			x	x	x	⁴ : Results for safety blood samples must be available and reviewed before drug is administered on Day 1, 3 and 6
Urine analysis	x	x		x			x			x	x	x	
ECG	x		x ⁵	x		x			x			x	⁵ : the baseline ECG should be conducted prior to dosing on Day 1, and subsequent ECGs should be taken at pre-dose on the rest of the dosing days and at time of visit on ambulatory visit days
SARS CoV antigen	x	x										x	

CONFIDENTIAL

Study Protocol

Study number: BV-01-101

Version No. : 3.0

Date: 13 Jul 2022

Visit	Screening (Days -28 to -2)	Day -1	Day 1	Day 2	Day 3	Day 4	Day 5	Day 6	Day 7	Day 8	Day 11	Day 14 (EOS)	
Viral screening (HIV, Hepatitis)	x												
Drug screening	x	x										x	
Breath alcohol test	x	x										x	
Weight/height (BMI)	x	x ⁶				x ⁶				x ⁶	x ⁶	x ⁶	⁶ : only weight
Plasma PK sample collection			x ⁷	x ⁸	x ⁸	x ⁸	x ⁸	x ⁸	x ⁷	x ⁸	x ⁸	x ⁸	⁷ : PK samples should be collected pre-dose and at 0.25, 0.5, 0.75, 1, 1.5, 2, 4, 8, 12 hr, on Day 1 and Day 7. Depending on ongoing PK data review, timepoints may be modified or removed. ⁸ : PK samples should be collected pre-dose on Day 2, 3, 4, 5 and 6 and 24hr +/- 30 min (Day 8), 96hr +/- 4hr (Day 11) and 168hr +/- 4hr (Day 14) after last dosing of Day 7.
PD ⁹			x ⁹	x		x ⁹	x		x ⁹	x			⁹ : PD blood sample should be taken pre-dose and at 1, 2, 4, 8, and 12 hr after dosing on Day 1, Day 4 and Day 7. One sample per day should be taken on Day 2 and Day 5 pre-dose, corresponding to 24 h after previous day dosing. One sample should be taken 24 h after previous day dosing on Day 8.
Adverse Events	x ¹⁰	x ¹⁰	x ¹⁰	x	x	x	x	x	x	x	x	x	¹⁰ : Adverse events occurring prior to study drug administration should be recorded as medical history unless the event is directly related to study specific procedure
Prior and/or Concomitant medications	x	x	x	x	x	x	x	x	x	x	x	x	

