The safety and tolerability of B-OT were assessed through a series of non-clinical toxicity studies, which included safety pharmacology investigations. The safety pharmacology investigations in rats (i.e., Irwin study) showed effects in female animals (1000 mg/kg/day) which were in a bad condition at the moment of the investigations. In the dog cardiovascular investigations, no effects on ECG by conventional ECG measurement. In a jacketed telemetry measurement, increases in heart rate were observed, at a supra-NOAEL dose level. In the same study no effect on respiratory functions were recorded.

Two-cycle (i.e., 1-week treatment followed by a 1-week treatment free period per cycle) repeat dose toxicity studies with B-OT were performed in rats and dogs. Female rats at the highest tested dose level (1000 mg/kg/day) were all prematurely euthanized on Day 7 of the study because of moribund condition. Other effects noted in the rats were lower body weight, transient hematological effects and some effects on cholesterol and triglyceride levels. In dogs one female animal was found dead on Day 5 in the second treatment cycle. Effects in surviving

animals were lower body weight and food consumption, which were partially reversed after a 1-week treatment-free period, as well as some transient changes in clinical pathology parameters. Furthermore, some non-adverse histopathological effects in thymus tissue were found. The No Observed Adverse Effect Level (NOAEL) for the rat study was set at 1000 mg/kg/day (males) and 300 mg/kg/day (females), and the NOAEL for the dog study was set at 0.15 mg/kg/day for both sexes.

Dosing is based on $\text{NOAEL} \times \text{HED} \times 1/10$ (No Observed Adverse Effect Level \times Human Equivalent Dose [dog/human] \times Safety Factor). As NOAEL was established in dog after a 7-day treatment and B-OT has already been used in compassionate use at a minimum daily dose of 3 mg for 7 days in 5 Covid-19 patients and 5 late-stage prostate cancer patients without any safety issue, only 3 subjects in the SAD part will receive the two first lowest doses.

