12.2.2 Procedures on Day -1

- Subjects will provide nasopharyngeal and/or oropharyngeal swab which will be tested for the presence of SARS-COV-2 infection with a rapid antigen test
- Subjects will arrive at the unit in the afternoon
- Subjects' eligibility will be re-checked and medical history re-reviewed
- Subjects will undergo a complete physical examination including documenting weight
- The Investigator will review any adverse events (AEs) that have occurred since the previous visit with the subjects
- Subjects will undergo a breath alcohol test
- Subjects will provide blood and urine samples for laboratory analysis (biochemistry, hematology, coagulation, urinalysis); the urine sample will be used also for drug screen test and cotinine test performed via dip stick
- Subjects will have their vital signs measured
- The Investigator will record any changes in concomitant medications or illnesses with the subjects since the last study visit
- Subjects will be admitted to the stationary unit of the site
- Subjects will receive unified balanced evening meal

12.2.3 Procedures on Day 1

- Subjects will be fasted from midnight (at least 10 hours fasting prior to dosing)
- Subjects will have their vital signs recorded (pre-dose)
- Subjects will undergo limited physical examination to target any change from the previous status or any body system deemed pertinent to Subjects by the PI (or designee) 4 hours post dose
- Subjects will undergo a 12-lead ECG pre-dose
- Subjects will receive a single dose of the assigned IMP (benfo-oxythiamine (B-OT)) within a time interval of two hours between 07:00 am and 09:00 am.
- Catheter for blood sampling will be inserted and serial blood samples will be collected for pharmacokinetic (PK) and pharmacodynamic (PD) analysis according to the sample schedule in section 12.4.1 Blood samples collection.
- Adverse events (AEs) that have occurred will be recorded
- Concomitant medication intake will be recorded
- Subjects will receive unified balanced lunch, afternoon snack and evening meal throughout the day

12.2.4 Procedures on Day 2

- Subjects will be fasted from midnight (at least 10 hours fasting prior to dosing)
- Subjects will have their vital signs recorded (pre-dose and approximately 4 hours after dosing)

- Subjects will undergo a limited physical examination to target any change from the previous status or any body system deemed pertinent to Subjects by the PI (or designee) 4 hours post dose

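### The MAD schedules no vital signs between the Day 1 dose and the Day 2 pre-dose set, so first-dose and Day 7 post-dose readings cannot be paired within subjects

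*Protocol*

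**What the plan says.** - **MAD default (protocol Table 2, footnote 2):** "if not otherwise indicated, VS should be taken either at pre-dose on dosing days or at time of visit on ambulatory visit days". The Day 1 cell carries no further footnote, so the default applies.
- **MAD exceptions (Table 2, footnote 3):** "on Day 2, 5 and 7, VS should be taken pre-dose and at 4 hr post-dose".
- **MAD visit text:** section 12.2.3 (Day 1) reads "Subjects will have their vital signs recorded (pre-dose" and closes the bracket there. Section 12.2.4 (Day 2) reads "Subjects will have their vital signs recorded (pre-dose and approximately 4 hours after dosing". Table and text agree, so this is not a slip in one place.
- **MAD ECGs (Table 2, footnote 5):** after the Day 1 pre-dose baseline, "subsequent ECGs should be taken at pre-dose on the rest of the dosing days". They supply no post-dose heart rate on dosing days.
- **SAD (Table 1, footnote 3):** "on Day1, VS should be taken pre-dose and at 2,4, 8 and 12 hr post-dose".
- **Role of vital signs:** they are part of the primary endpoint (protocol 11.1). They are summarised descriptively with change from baseline, and baseline is the last value before dosing (protocol 14.7 and 14.8.2; SAP 6.2 and 11.3).
- **Non-clinical background (protocol 8.3):** "In a jacketed telemetry measurement, increases in heart rate were observed, at a supra-NOAEL dose level".

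**The concern.** The multiple-dose part exists to show what repeated dosing adds to a first dose. For PK, the protocol builds that contrast into each subject: full profiles on Day 1 and Day 7, and Day 7/Day 1 accumulation ratios. PD is also profiled on both days. Post-dose vital signs, a primary safety measure, are not paired in this way, and the documents give no reason for going from four first-day sets in the SAD to none.

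The study has no control arm, so nothing else separates a drug effect from time of day, confinement or sampling procedures. A subject's own Day 1 post-dose change would be the natural reference for the Day 7 change. The drug's active metabolite is described as an irreversible enzyme inhibitor, which makes change over repeated doses a fair question. The dog heart-rate increase occurred above the NOAEL; it supports looking at pulse but does not imply an effect at these doses.

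**Working it through.** No sample-size or power figure bears on this, so the check is of the schedule.

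**1. Post-dose sets by dosing day** (protocol Tables 1, 2 and 4)

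| Dosing day | Post-dose vital signs | Post-dose PK/PD times, up to 12 h |
|---|---|---|
| SAD Day 1 | 2, 4, 8, 12 h | PK 9, PD 5 |
| MAD Day 1 | none | PK 9, PD 5 |
| MAD Day 2 | 4 h | none |
| MAD Day 3 | none | none |
| MAD Day 4 | none | PD 5 |
| MAD Day 5 | 4 h | none |
| MAD Day 6 | none | none |
| MAD Day 7 | 4 h | PK 9, PD 5 |

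First-day total: SAD 4, MAD 0. Over the seven MAD doses: 3 sets, all at 4 h. Day 7 is the only MAD day on which a post-dose vital-sign set coincides with post-dose PK sampling.

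**2. Length of the gap.** Input: each MAD dose is given "within a time interval of two hours between 07:00 am and 09:00 am".
- Day 1 dose to the Day 2 pre-dose set: shortest 24 + (7 − 9) = 22 h, longest 24 + (9 − 7) = 26 h. If pre-dose vital signs are taken 35 min before dosing (an assumption, borrowed from the PK pre-dose time), this becomes 21.4 to 25.4 h.
- Day 1 dose to the first set timed after a dose (Day 2, 4 h): 22 + 4 = 26 h to 26 + 4 = 30 h. By then the second dose has been given.

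The gap applies to all 4 × 6 = 24 MAD subjects, including the 4 sentinels.

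**3. What else is scheduled on Day 1.** There is a limited physical examination at 4 h (12.2.3). Section 12.3.3 lists body systems, including cardiovascular, but not pulse or blood pressure as recorded items.

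**4. Which comparisons remain.**
- *Planned:* the 4 h value on Day 2, 5 or 7 minus the Day 1 pre-dose value. This sets a reading at 11:00–13:00 (07:00–09:00 plus 4 h) against an early-morning one from an earlier day.
- *Between subjects:* the MAD Day 7 change at 4 h against the SAD Day 1 change at 4 h, at the same dose. Planned numbers are 6 against 3 at 1 mg, and 6 against 6 at 2, 3 and 5 mg (24 MAD and 3 + 6 + 6 + 6 = 21 SAD subjects).
- *Within subject (missing):* (Day 7 4 h − Day 7 pre-dose) − (Day 1 4 h − Day 1 pre-dose). Time-of-day effects that are the same on both days cancel, and so do stable subject differences.

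To size the loss, let each same-day change have variance σ², and let a subject's Day 1 and Day 7 changes have correlation ρ. Neither value is in the documents.
- Between-subject variance: σ²(1/6 + 1/3) = 0.50σ² at 1 mg; σ²(1/6 + 1/6) = 0.33σ² at the other doses.
- Within-subject variance: 2σ²(1 − ρ)/6 = 0.33σ²(1 − ρ) at every dose.

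At 1 mg the pairing is more precise even at ρ = 0. At the other doses it is more precise whenever ρ > 0. It also removes differences between the SAD and MAD groups, which the between-subject comparison cannot.

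**The case against.** The case on the other side is substantial, and most of it stands.

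- **A reader might infer that the first-dose response is never measured.** The documents do not support that. All four MAD doses were given as single doses in the SAD with four post-dose sets, and protocol 6.1 reports good tolerability with no side effects detected. Section 12.3 also allows any safety procedure at any time. In the MAD, the readings are unscheduled.
- **A reader might infer that first-dose and Day 7 responses cannot be compared at all.** They can, between subjects and by dose. Neither document plans a within-subject comparison, and change from the last value before dosing is the specified method.
- **A reader might infer that sentinel release rests on one set of vital signs.** By 72 h the sentinel also has vital signs about 24 h after each dose (Days 2, 3 and 4 pre-dose), examinations at 4 h on Days 1 to 3, a Day 2 ECG, and Day 2 laboratory results reviewed before the Day 3 dose. It remains true that the only set within hours of a dose follows the second one.
- **A reader might argue that 4 h misses the peak**, because mean tmax was 1.67 to 2.50 h. The upper figure is 2.50 ± 1.18 h, and the sampling grid runs from 2 h to 4 h. A mean above 2 h therefore requires some subjects to have peaked at 4 h or later, so 4 h is not an uninformative time.
- **A reader might suspect that lunch, at about 4 h, distorts that set.** Nothing says which comes first, and the SAD shares the timing.

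Section 8.6.4 also lets assessments be added for later cohorts. That provides a route to the change but does not schedule it.

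**Conclusion.** The gap is real and consistent across Table 2 and section 12.2.3: no scheduled vital signs for about 22 to 26 h after the first MAD dose, in all 24 subjects. The consequence is limited. The plan gives up the within-subject, time-matched comparison of Day 1 and Day 7 post-dose vital signs, and it schedules no reading within hours of a dose in the sentinel until 26 to 30 h after the first dose, once the second has been given. It does not leave any dose level unobserved. This is an inexpensive improvement to an uncontrolled design and does not show that the study is unsafe. The figures assume planned cohort sizes, the stated dosing window and no unscheduled readings. Discretionary readings would help individual subjects but would not give complete, comparable data.

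**What to change.** - **Schedule:** in Table 2 and section 12.2.3, add a vital-sign set at 4 h on Day 1. It matches the existing Day 7 set and coincides with the Day 1 examination and blood draw. Preferably also add 2 h sets on Days 1 and 7 (sections 12.2.3 and 12.2.9), which restores the SAD's 2 h and 4 h times.
- **Analysis:** in SAP 11.3 and the MAD vital-signs table, show the Day 1 and Day 7 changes from that day's own pre-dose value side by side by dose, next to the planned change from baseline.
- **If a cohort has already been dosed without the Day 1 set:** tabulate its Day 7 4 h same-day change beside the SAD Day 1 4 h same-day change at the same dose, labelled as between-subject. This needs no new data.
- **If the schedule is kept:** state why Day 1 has no post-dose set when the SAD had four.

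**Cost:** one extra reading per subject for the minimum change and three for the preferred one, or 24 to 72 across 24 subjects. Subjects are confined, blood is already drawn at these times, and no blood volume or visit is added. The protocol needs a small amendment. Vital-sign changes are not among those that section 15.6.2 defines as non-substantial, so the sponsor must classify it.
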